This study is designed as an observatory field study of characterizing younger and older adults' everyday life in terms of light exposure patterns as well as cardiovascular, metabolic and psychological health parameters over 10 days continuously through wearables and smartphone-based self-reports (ambulatory assessment period). On the first day of data collection, each participant will undergo an eye examination at the Institute of Ophthalmology. Thereafter participants start wearing the wearable sensors and instructions on how to complete the smartphone-based self-report forms are provided. Data will be collected from the first evening onwards (ca. 18:00 h). After the ambulatory assessment period under free-living conditions, participants will spend the 11th and 12th day in a controlled office room environment from 08:30 to 17:00 h. In a randomized cross-over design, the 11th and 12th day will be spent in either bright (1250 lux) or dim office lighting (10 lux). On these days, participants will continue to wear the wearables and complete the same smartphone-based self-reports as over the 10-day ambulatory assessment period. Between day 11 and 12, participants will leave controlled conditions from 17:00 h on day 11 to 08:30 h on day 12. On day 11 and 12, participants will receive a standardized fluid meal for breakfast and a bread-based meal for lunch, and are otherwise instructed to avoid any food, caloric or caffeinated beverages between 08:30 and 17:00 h. After removing all wearables on day 12, the study ends at 17:30 h. Over these 12 days of data collection, participants will be asked to keep their bedtimes at home as consistent as possible between days, and on day 11 and 12 they will be instructed to come to the office facilities fasted without any caloric intake after 22:00 h on the previous evening of day 10 and 11, respectively.

To minimize the burden on participants in this study, we use mobile and user-friendly devices for data collection and give clear instructions for data collection. We keep individual assessments short, limit the study duration to 12 days and provide incentives for participation (up to €200 reimbursement). On day 11 and 12, participants are mostly free to do whatever they like to do while being in the office environment (e.g. watching movies, paperwork, reading, video-meetings etc.).

[figure not shown]

Fig.1. Overview of study design.

4. Responsibilities

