4.4. Registration

The study will be registered on osf.io.

5. Participants

30 healthy younger adults and 30 healthy older adults.

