6.2. Participants and Groups

The two comparative groups formed in this study consist of 30 younger adults (18-35 years) and 30 older adults (60-80 years), both females and males will be included, and the aim is to match both groups with respect to sex (i.e. ideally 15 women and 15 men per group). The age contrast in the two groups is chosen, as substantial differences in degeneration of the lenses and retina within the eye can be expected.

For the sample size calculation of $n = 30$ per group, we refer to Zauner et al. (Zauner et al., 2023), who created a procedure to calculate statistical power and required sample size for wearable light-logging data. For most light-logging metrics, their approach shows that for strong differences in light exposure patterns (i.e., winter vs. summer) even smaller samples are sufficient ($n = 3-24$). We do not expect that differences between age groups are that strong as seasonal differences. However, we are confident that effects of about $d = 0.7$ could be detected with our design ($n = 30$ per group).

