6.4 Measurement devices

All measurements within the framework of the research project are non-invasive, except for placing a continuous glucose monitor on the non-dominant forearm of participants from day 1 of the data collection period onwards.

Table 3 shows the different types and respective resolutions of the recorded data.

The continuous glucose monitor and the light sensor will be worn throughout the 12 days of the study, while the thermal skin sensors and the ambulatory blood pressure device will only be worn on day 11 and 12, between 08:30 and 17:00 h respectively.

Table 3. Data collected, methods and resolution.

Data	Unit	Device name	Frequency
Skin temperature	°C	iButtons	1 min
Interstitial glucose	mmol/L	Abbott Freestyle Pro IQ	15 min
Illuminance	Lux Melanopic EDI	Actlumus	1 min
Blood pressure	mmHg	ECGpro Holter-RR USB	15 min

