8.3 Descriptive statistics

Statistical analysis will be performed using the statistical computer programs SPSS for Mac OS (version 25, IBM) and R Studio for Windows. Descriptive statistics will be reported for all data parameters and will be reported as minimum, maximum, mean, standard deviation (SD) and intraindividual standard deviation (iSD) for data assessed in daily life, and/or standard error of the mean (SEM). As a measure of dispersion, SD will be used for descriptive statistics of the assessed data, while the SEM will additionally be reported for the results of the primary and secondary outcomes.

In case of non-normality, values will either be transformed using log transformation or non-parametric tests will be used. In addition, Pearson correlation coefficients will be computed to correlate parameter values. The unpaired Students t-test will be used to compare outcome measures between the young and old group. Due to the randomized cross-over design, to compare outcomes between the bright and dim office light condition irrespective of age (secondary outcome), a paired t-test will be conducted. Differences will be considered statistically significant when tested two-sided $p < 0.05$. Missing values will not be replaced. We will apply a full information approach using all available data from all participants.

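### For glucose, the planned paired t-test of bright versus dim leaves unused the fasting readings recorded before both sessions: a missed precision gain, not an invalid test

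*Protocol*

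**What the plan says.** The design section (3) states: "In a randomized cross-over design, the 11th and 12th day will be spent in either bright (1250 lux) or dim office lighting (10 lux". Section 8.3 fixes the analysis: "to compare outcomes between the bright and dim office light condition irrespective of age (secondary outcome), a paired t-test will be conducted". It names no covariate and no pre-session value. The mixed models in section 8.4 relate daily light exposure to health parameters and are not given as the bright-versus-dim analysis.

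On what is recorded before each session:

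- **Glucose.** Section 6.4 says "The continuous glucose monitor and the light sensor will be worn throughout the 12 days of the study", and Table 3 gives one reading every 15 minutes. Section 3 has participants arrive on days 11 and 12 without calories since 22:00 the evening before. Fasting readings before 08:30 therefore exist on both mornings.
- **Blood pressure and skin temperature.** Section 6.4 limits these devices to 08:30 to 17:00 on the two office days, so they have no pre-session value.
- **Self-reports.** Section 6.3.4 gives six prompts a day without clock times, so a prompt before 08:30 is not assured.

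On the preceding hours, day 10 is free-living, and section 3 adds that "participants will leave controlled conditions from 17:00 h on day 11 to 08:30 h on day 12". The same section asks for consistent bedtimes and provides standardised meals on both office days.

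**The concern.** Each condition is observed on a single day per person, so no averaging over days reduces day-to-day variation. Evening food before 22:00, activity and actual sleep can differ between the nights before day 11 and day 12. If they shift fasting glucose, and fasting glucose predicts glucose during the session, that shift enters the bright-minus-dim difference. A plain paired t-test leaves it in the error term although the data to remove much of it are already collected.

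The cross-over is the study's only randomised comparison, and the protocol states no effect size, standard deviation or power for it. Precision that costs no extra measurement is therefore worth taking.

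**Working it through.** **The plan's own figure.** Section 6.2 says "we are confident that effects of about $d = 0.7$ could be detected with our design ($n = 30$ per group". This concerns young versus old. With d = 0.7, two-sided 0.05 and 30 per group, power is 76.0% (t) or 77.4% (normal approximation), and 80% power would need 34 (t) or 33 (normal) per group. The section states no power and says only about 0.7, so the figure can be neither confirmed nor called wrong. It does not cover bright versus dim.

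**Inputs for bright versus dim.**

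- Pairs: section 5 gives "30 healthy younger adults and 30 healthy older adults", so n = 60 irrespective of age.
- Significance rule, section 8.3: "Differences will be considered statistically significant when tested two-sided $p < 0.05".
- r, the correlation between the bright-minus-dim baseline difference and the bright-minus-dim session difference: not in the protocol, assumed from 0 to 0.7.
- True effect: not in the protocol, set so that the plain paired t-test has 80% power. With 59 degrees of freedom this is dz = 0.368, a mean difference of 0.368 SD of the differences.

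**Formulas.** Regressing the session difference on the baseline difference and reading the intercept multiplies the variance of the estimate by f = (1 − r²)(1 + 1/57). The second factor is the price of estimating the slope with n = 60. Power comes from the noncentral t with 58 degrees of freedom and noncentrality dz × √60 / √f. The plain test needs 60/f pairs to match. A simple change score has variance factor 2(1 − r), assuming that the baseline and session differences have equal variances.

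Example at r = 0.5: f = 0.75 × 1.0175 = 0.763. The noncentrality rises from 0.3677 × 7.746 = 2.85 to 2.85/0.8735 = 3.26. Power is 89.4%, and 60/0.763 = 78.6 pairs.

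| r (assumed) | f | Adjusted power | Detectable dz at 80% | Pairs the plain test needs to match | Change-score power |
|---|---|---|---|---|---|
| 0 | 1.018 | 79.3% | 0.371 | 59 | 50.8% |
| 0.2 | 0.977 | 80.9% | 0.364 | 61 | 60.1% |
| 0.3 | 0.926 | 82.9% | 0.354 | 65 | 65.8% |
| 0.5 | 0.763 | 89.4% | 0.321 | 79 | 80.0% |
| 0.7 | 0.519 | 97.3% | 0.265 | 116 | 95.1% |

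In variance, adjustment breaks even where (1 − r²)(58/57) = 1, that is r² = 1 − 57/58 = 0.0172, or r ≈ 0.13.

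**Validity.** In simulation (8,000 runs per setting, n = 60, no carry-over) the plain test had type I error of 4.5% to 5.2% and a mean estimate near 0 at every r. The SD of the estimate fell with adjustment from 0.130 to 0.114 at r = 0.5 and from 0.129 to 0.094 at r = 0.7. At r = 0 it rose from 0.130 to 0.131.

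**Carry-over.** Suppose bright light on day 11 shifts the day-12 baseline by 0.3 SD (assumed), with r = 0.5. Half the participants have bright first, so the mean baseline difference moves by 0.5 × 0.3 = 0.15, and times the slope of 0.5 this is about 0.07 SD.

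- If the shift runs through to the session outcome, the unadjusted estimate is off by −0.07 SD and adjustment removes the error.
- If only the baseline shifts, the unadjusted estimate is right and adjustment adds +0.07 SD.

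**The case against.** The strongest reply is that nothing here is wrong: the paired t-test is a valid analysis of a randomised cross-over, and covariates are often left to a statistical analysis plan. The first half stands. A reader might infer that differences from the night before contaminate the comparison systematically. The protocol does not support that: order is randomised, so without carry-over they are noise, and the fast, the bedtime request and the standardised meals limit even the noise. The second half does not dispose of the point, because section 8.3 names the test.

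Section 8.3 also leaves the office-day glucose variable undefined, and it could already be a change from the fasting level. That does not remove the gain. Covariate adjustment is at least as precise as a change score apart from one degree of freedom, and a change score loses to the plain comparison when r is below 0.5.

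The gain rests on an unknown r. This stands: there is a slight loss at r = 0 and almost no gain at 0.2. A reader might infer that every glucose interval would tighten, which cannot be claimed.

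Finally, the second baseline is measured after the first light session, so adjustment has its own bias risk. This stands too and is why both estimates should be shown.

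**Conclusion.** The point holds for glucose only, as a missed precision gain on a secondary outcome. Against 80% power for the plain test, adjusted power runs from about 79% at r = 0 to 97% at r = 0.7. The downside is under one percentage point of power, and the gain becomes material from about r = 0.4 (85.8%). These figures assume 60 complete pairs, a linear relation and no carry-over; r is an assumption throughout.

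Two wider readings are not supported. First, the point does not extend to blood pressure or skin temperature, which have no pre-session value, nor to self-reports unless a prompt falls before 08:30. Second, a reader might take the adjustment as yielding a better measure of each person's light sensitivity. It gives one group-level intercept, not an adjusted value per person.

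**What to change.** In section 8.3, specify for glucose a regression of each person's bright-minus-dim session difference on the bright-minus-dim difference in fasting glucose before 08:30. Enter the baseline difference as a covariate, do not form a change score, and report the effect at zero baseline difference with its interval. Fix the baseline window in advance, for example the mean of the 07:30 to 08:30 readings (about four at 15-minute spacing). Report the unadjusted paired t-test alongside and say that a gap between the two may reflect carry-over from day 11.

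Keep the plain paired t-test for blood pressure and skin temperature, and for self-reports unless a prompt before 08:30 is scheduled on both office days.

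The cost is one analysis sentence and one degree of freedom, with no new measurement. Participants without readings in the window on both mornings would drop out of the adjusted analysis but remain in the unadjusted one.

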8.4 Primary and secondary study parameters

As the primary hypothesis of this study is that younger and older individuals differ in their light exposure patterns in everyday life, the primary outcome of this study is melanopic equivalent daylight illuminance (M-EDI) quantified in lux by the Actlumus wearable light sensor. M-EDI may differ between groups with respect to overall daily levels, exposure levels at different times of day (work-day vs. weekend-day), and the difference in exposure levels between work-days and weekend-days. Therefore, M-EDI will be statistically analysed between groups in the following three ways:

1. Compare the area under the curve (AUC) of M-EDI from day 1 to day 8 between young and old (unpaired t-test)

2. Averaging exposure levels over work-days and weekend-days in 1-hour time intervals over 24 hours and compare the two average 24-hour M-EDI patterns between young and old (2-way repeated measures ANOVA, factor 1 (between-subjects) group, factor 2 (within-subjects) time)
3. Averaging the onset of M-EDI in the morning hours and the offset in the evening over work-days and weekend-days and calculate the difference in onset and offset between the averaged work-day and weekend-day between groups (unpaired t-test)

The secondary hypotheses are that light exposure patterns in everyday life are linked to daily metabolic, cardiovascular and psychological outcomes, and that this link is stronger in individuals displaying less degeneration of eye structures.

Accordingly, mixed effects regression analyses will be performed to assess the relationship between different aspects of daily light exposure (momentary M-EDI, average daily exposure level, onset/offset; independent variables) and each of the daily health parameters (metabolic, cardiovascular, psychological functioning, and sleep; dependent variables). To evaluate the role of the degree of eye degeneration, an interaction term between light exposure and eye degeneration will be added to the regression models.

9 Ethics

The study must be approved by the Ethics Committee of RWTH Aachen University. The study is carried out in accordance with the Declaration of Helsinki (the latest version, established in Fortaleza, Brazil, 2013) and the Law on Medical Research involving Human Beings (WMO) and the General Data Protection Regulation (GDPR or GDPR).

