Growing evidence suggest that the effects of light on health parameters vary dramatically across individuals, yet recommendations for appropriate light exposure in real-life settings rarely take these individual differences into account (Chellappa, 2021). In this context, age has been identified as a moderator of light sensitivity (Chellappa, 2021), but the underlying mechanisms remain elusive. Therefore, this interdisciplinary project will for the first time explore the contribution of aging processes within the eye to an individual's sensitivity to light and its health effects. The degeneration of the lens associated with cataract is a natural aging process that affects the amount of light that can reach the retina. Cataract affects around 17% in the general population worldwide and up to 54% in the over-60 age group (Hashemi et al., 2020). Replacing the lenses of the eye by surgery largely restores light transmission and has been shown to improve the sleep-wake rhythm, the release of the sleep hormone melatonin, light sensitivity, and sleep quality (Brøndsted et al., 2017; Giménez et al., 2016). Depending on how far the degeneration of the lens and retina have progressed and/or whether surgical intervention has taken place, large individual differences in sensitivity to different ambient light can therefore be expected. However, this aging process is ignored by most previous attempts to study the physiological and psychological health effects of light.

2. Aim of the study

With the primary hypothesis of this study being that younger and older individuals differ in their light exposure patterns in everyday life, the two main goals of the AgeLight study are to:

- characterize light exposure patterns in younger and older adults and their link to cardiovascular, metabolic, and psychological health
- identify determining factors of an individual's sensitivity to light and its health effects (such as degeneration of the lens and retina)

3. Study design

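### Section 8.4 tests one primary hypothesis with three unranked analyses, and none of them tests the announced work-day versus weekend-day difference in exposure level

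*Protocol*

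**What the plan says.** Section 2 states one primary hypothesis: "With the primary hypothesis of this study being that younger and older individuals differ in their light exposure patterns in everyday life". Section 8.4 repeats it and names melanopic equivalent daylight illuminance (M-EDI) as the primary outcome. M-EDI is a measured quantity, not yet a test.

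Section 8.4 then lists three respects in which the groups may differ: overall daily level, level at different times of day, and "the difference in exposure levels between work-days and weekend-days". From these it concludes that "M-EDI will be statistically analysed between groups in the following three ways":

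1. An unpaired t-test of the age groups on the M-EDI area under the curve (AUC), pooled over days 1 to 8.
2. Hourly averages over work-days and weekend-days, used to "compare the two average 24-hour M-EDI patterns between young and old" in a two-way repeated measures ANOVA with "factor 1 (between-subjects) group, factor 2 (within-subjects) time".
3. Morning onset and evening offset of M-EDI, averaged by day type, in order to "calculate the difference in onset and offset between the averaged work-day and weekend-day between groups (unpaired t-test").

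The numbers only list the analyses. Section 8.4 names no lead analysis and no testing order, and does not say whether one significant result or all of them would support the hypothesis. Section 8.3 gives the general criterion: "Differences will be considered statistically significant when tested two-sided" p < 0.05.

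**The concern.** There are two separate problems.

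**No lead test.** One hypothesis sits on several tests, each at 5%. Without a named primary test or a rule for combining them, a reader of the results cannot tell what would count as confirmation. If one significant result among several sufficed, the hypothesis could be declared supported by chance more often than the stated 5%.

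**An announced contrast without a test.** The third facet in Section 8.4 is a difference in exposure level between day types. The analysis that contrasts day types looks at when light exposure starts and stops, not at how much light there is. Carrying out the plan exactly would leave this facet of the primary outcome without a direct answer. This problem does not depend on any view about multiplicity.

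**Working it through.** **Step 1: count the group-related p-values in Section 8.4.**

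- Analysis 1 gives one (AUC).
- Analysis 2 gives at least one. A two-way ANOVA yields both a group effect and a group-by-time effect.
- Analysis 3 most plausibly gives two, one for onset and one for offset. The text names a single t-test, so one is possible.

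The total is 1 + 1 + 2 = 4 on the likelier reading, and 1 + 1 + 1 = 3 on the narrowest.

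**Step 2: chance of at least one false positive.** The inputs are alpha = 0.05 two-sided (Section 8.3) and k = 3 or 4 (step 1). Two assumptions are not in the protocol: that any one significant result counts as support, and the correlation between the test statistics.

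For independent tests the formula is 1 − 0.95^k:

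- k = 3: 1 − 0.8574 = 14.3%
- k = 4: 1 − 0.8145 = 18.5%

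For equally correlated normal test statistics with correlation ρ, the chance is 1 − P(all |Z| ≤ 1.96), by numerical integration:

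| Tests | ρ = 0 | ρ = 0.5 | ρ = 0.7 | ρ = 0.9 |
|---|---|---|---|---|
| 3 | 14.3% | 12.5% | 10.9% | 8.4% |
| 4 | 18.5% | 15.6% | 13.0% | 9.4% |

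For k = 4, simulated two-sample t-tests with 30 per group give 18.5, 15.5, 13.0 and 9.5%, so the normal approximation is adequate. Every entry exceeds 5%.

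**Step 3: higher counts are illustrative only.** If both ANOVA effects are read, the count is 1 + 2 + 2 = 5. If work-day and weekend-day patterns also get separate ANOVAs, it is 1 + 4 + 2 = 7. Independence would give 22.6% and 30.2%, but it is not credible here, because the AUC largely repeats the ANOVA group effect. With one ANOVA, five tests behave nearly like four, so the ceiling falls to about 18.5%. With two ANOVAs, treating the AUC as a 5:2 weighted combination of the work-day and weekend-day group effects (an assumption) and the other six tests as independent, simulation gives 27.5%.

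**Step 4: which analysis tests the day-type contrast in level?** For each person let W be the mean work-day level, E the mean weekend-day level, and D = W − E. The announced comparison is whether mean D differs between the age groups, that is, the group difference in W minus the group difference in E.

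- *Analysis 1* pools days 1 to 8. With assumed 5:2 weights it responds to 5W + 2E. Raising W by 2δ and lowering E by 5δ leaves that sum unchanged (10δ − 10δ = 0) but moves D by 7δ. The AUC can therefore miss the contrast entirely.
- *Analysis 2* has group and time of day as its only factors. Running it separately by day type would compare the groups on W and on E. A significant result on one day type and not on the other is not a test of the difference between them.
- *Analysis 3* does contrast work-days with weekend-days by group, but on onset and offset, which are clock times and not levels in lux.

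No listed analysis compares D between the groups.

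**The case against.** **The study is largely descriptive, and the text leans towards a facet-by-facet reading.** Section 3 calls it an observational field study, the age comparison is not randomised, and Section 8.4 moves from three facets to three analyses, roughly one each. Read that way, the inflation in step 2 does not arise in that form. This stands, and a reader who infers that a 5% error rate has been shown to be breached goes further than the protocol supports. What remains is that the protocol does not say which reading applies.

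**The count can be overstated.** A reader might infer seven tests and a risk of 30%. The documents do not support that as a headline. The two average patterns may mean one for young and one for old, hence a single ANOVA, and the AUC overlaps the group effect. The figures for three and four tests are the ones to use.

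**Some of this is analysis-plan detail.** A multiplicity adjustment, the number of ANOVAs and the choice of effect may properly be left to a statistical analysis plan, which may exist and is not shown. Their absence is not criticised here. The protocol itself, however, fixes the three analyses under one primary hypothesis without a lead, and the mismatch between level and timing lies within Section 8.4.

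**The day-type point may be only a phrase.** Section 8.4 says M-EDI may differ in that respect and does not list a test of it; the authors may have meant timing. That is possible, and rewording would then settle it. As written, the announced facet and the analysis do not match.

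**Conclusion.** The concern holds in two parts, and the protocol should be changed on both.

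First, one primary hypothesis rests on three unranked analyses giving most plausibly at least four group-related p-values, or three at the narrowest, each at two-sided 0.05. Conditional on a rule that any one significant result suffices, the false-positive risk is about 8-14% for three tests and 9-19% for four. That range rests on the assumed rule and on assumed correlations from 0.9 down to 0. The firm finding is that the lead test and the rule of interpretation are unstated.

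Second, the announced group comparison of the work-day versus weekend-day difference in exposure level has no direct test among the three analyses. This follows from the wording alone and needs no numerical assumption.

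**What to change.** In Section 8.4:

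1. Name one primary test at two-sided 0.05. The choice is the investigators'; the AUC comparison, listed first, is one candidate.
2. Label the remaining M-EDI analyses secondary and state that each is interpreted for its own facet. A fixed order or a Holm adjustment is optional and, if used, should cover these M-EDI analyses only, not the light-health regressions or the bright versus dim comparison.
3. Add a between-group t-test of each participant's work-day minus weekend-day M-EDI level, which is equivalent to a group-by-day-type test. If timing was meant, correct the announced contrast to onset and offset instead.

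**Cost.** The non-primary analyses no longer count on their own as confirmation of the primary hypothesis, and there is slightly more analysis work. No extra participants or measurements are needed, and the named primary test keeps its full 5%. If Holm is chosen for four secondary p-values (for example one ANOVA effect, onset, offset and the added level contrast), the first step is 0.05/4 = 0.0125. With 30 evaluable per group, the difference detectable with 80% power in a two-sample t-test then rises from 0.74 to 0.89 SD at that step. This figure applies to the t-tests and not to the ANOVA effects.

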
1. Background

Within a day, the Earth rotates once around its own axis, causing predictable changes in light conditions throughout the day. In this context, humans have developed the ability to synchronize their physiological processes to a period length of around 24 hours, adapting to these recurring fluctuations. Our ambient light hence has a major influence on our physiology and psychology depending on the time of day. However, over the last century our relationship to light has drastically changed: our current “indoor society” spends about 90% of awake time indoors exposed to lower light intensities (e.g. up to 300 lux for typical electric office lighting) than outside in natural daylight (e.g. up to 100,000 lux on a sunny day), along with excessive exposure to artificial light during the evening beyond sunset. Yet, studies on the impact of daytime light exposure patterns are limited (Fleury et al., 2020). A chronic lack of daylight in combination with excessive light in the evening is increasingly being considered as a risk factor in the aging society's rising incidence of cardiovascular, metabolic, and psychological disorders. For example, experiencing darker days and brighter nights was associated with a higher risk for the onset of several psychological disorders such as depression or psychosis (Burns et al., 2023). In terms of short-term effects on potential mediating mechanisms, Harmsen et al. previously showed that bright light during office hours induced mostly favorable acute effects on glucose control and thermoregulation in older insulin-resistant volunteers compared to dim light (Harmsen et al., 2022) and that natural office lighting through windows improved glucose control in older type 2 diabetes patients (Harmsen et al., 2022). Similarly, when workers were exposed to higher levels of light during their workday, they reported increased vitality and lower depressive symptoms (Mariana G. Figueiro et al., 2017; Nagare et al., 2021). However, to date, there is only limited data on how light exposure patterns differ across the lifespan (Scheuermaier et al., 2010) and how aging may affect the influence of light on our physiology and psychology. First findings indicate that younger and older adults show different emotional effects of exposure to blue light (Sletten et al., 2009), but these differences have so far not been addressed in daily life.

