6.1. Study Timeline

The study will be conducted between November 2024 and May 2025.

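### Two primary M-EDI tests ignore measurement date, and nothing schedules young and old over the same weeks: lost precision if timing is balanced, bias if it is not

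*Protocol*

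**What the plan says.** Protocol section 8.4 makes melanopic EDI (M-EDI) the primary outcome and names three between-group analyses:

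1. "Compare the area under the curve (AUC) of M-EDI from day 1 to day 8 between young and old (unpaired t-test").
2. For the hourly pattern: "Averaging exposure levels over work-days and weekend-days in 1-hour time intervals over 24 hours", with the resulting curves then tested in a "2-way repeated measures ANOVA, factor 1 (between-subjects) group, factor 2 (within-subjects) time". Time here is clock hour, not date.
3. An unpaired t-test on each person's work-day to weekend-day difference in light onset and offset.

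Section 8.3 repeats the unpaired t-test for young versus old. Section 6.1 states: "The study will be conducted between November 2024 and May 2025". Section 3 says the investigators "limit the study duration to 12 days", so each person contributes one short block somewhere in that window. On the groups, section 6.2 says "the aim is to match both groups with respect to sex" and names no other matching factor. On season, it says: "We do not expect that differences between age groups are that strong as seasonal differences". Sections 5.3, 5.4, 6.5 and 9.3, on scheduling and recruitment, say nothing about measuring the two age groups over the same calendar weeks.

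**The concern.** The outcome is the light that reaches a person, and section 6.2 ranks season above age as a determinant of it. Day length roughly doubles across the study window, yet analyses 1 and 2 have no term for it and the design does not balance it.

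There are two distinct consequences:

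- **Dates unrelated to age group.** Both tests are valid, but seasonal variance that known dates could explain stays in the error term.
- **Enrolment of the two groups drifts apart.** Part of the apparent age difference is then a difference in day length, and the tests as written can neither show nor remove it. In the hourly model it appears as a false group-by-time interaction around dawn and dusk.

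Analysis 3 is much less exposed, because each person is their own control over a few days.

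**Working it through.** **Inputs from the protocol.** 30 per group, d = 0.7 (section 6.2); two-sided 0.05 (section 8.3); November 2024 to May 2025 (section 6.1); AUC over days 1 to 8 (section 8.4).

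**Assumptions.** Latitude is 50.8 N. Start dates run from 1 November to 20 May (201 dates). The seasonal effect D is the rise in AUC from the shortest to the longest days, in units of the season-free SD, set at 0.7, 1.0 and 1.5. The protocol gives no value.

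**Step 1: the plan's own figure.** With n = 30 per group and d = 0.7, the unpaired t-test has 76.0% power (noncentral t). The protocol states no power, so there is nothing to confirm or refute.

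**Step 2: day length.** Averaged over days 1 to 8, it runs from 7.95 to 15.88 h, a range of 7.93 h. It is scaled to S between 0 and 1. With dates drawn independently of group, the gap between group means has SD 0.67 h. Hence SD(S) = 0.67 / √(2/30) / 7.93 = 0.327 and var(S) = 0.107.

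**Step 3: variance due to season.** The share is D²·var(S) / (1 + D²·var(S)):

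- D = 0.7: 0.052 / 1.052 = 5%
- D = 1.0: 0.107 / 1.107 = 10%
- D = 1.5: 0.241 / 1.241 = 19%

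**Step 4: bias under a shift.** If one group's window is 30 days later, mean day length differs by 1.14 h. Bias = D × 1.14 / 7.93 = D × 0.144, which is 0.10, 0.14 and 0.22 SD.

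**Step 5: AUC test by simulation.** Model: Y = D·S + N(0,1), 40,000 trials per setting. The t-test is compared with a linear model of group plus S. Values are for D = 0.7 / 1.0 / 1.5.

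| Timing | t-test type I error, % | t-test power at d = 0.7, % | Adjusted power, % |
|---|---|---|---|
| Dates independent of group | 5.0 / 4.9 / 5.0 | 74 / 72 / 67 | 75 |
| 15-day shift | 5.4 / 5.8 / 6.2 | not tabulated | 75 |
| 30-day shift | 6.4 / 8.4 / 11.7 | 61 / 53 / 39 if bias opposes the age effect; 85 / 87 / 89 if it adds to it | 73 |
| 60-day shift (unlikely extreme) | 13 / 22 / 40 | not tabulated | about 60 |

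The adjusted test's type I error is 4.9 to 5.2% throughout. If the true effect follows √S or S² instead of S, the residual bias after linear adjustment is at most 0.035 SD (30 days, D = 1.5), against 0.17 to 0.22 SD unadjusted.

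**Step 6: exactly matched dates.** Season then cancels from the group difference but still inflates the t-test's error term. The plain t-test becomes conservative, with type I error about 4.5 / 3.9 / 3.1%.

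**Step 7: hourly ANOVA, group-by-time.** A daylit hour is assumed to be 0.5 / 1.0 / 1.5 SD brighter than a dark one. Errors are a person effect (variance share 0.3) plus AR(1) with 0.6, with Greenhouse-Geisser correction.

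| Timing | Type I error, % |
|---|---|
| Dates independent of group | 4.3 / 4.2 / 4.2 |
| 15-day shift | 4.3 / 4.7 / 6.0 |
| 30-day shift | 4.9 / 7.6 / 14.0 |
| 60-day shift | 8 / 30 / 65 |

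With day length and its interaction with time in the model, type I error is 3.9 to 4.3% in all of these. With independent dates, power for a 0.7 SD group difference confined to three evening hours is 69 / 66 / 61% unadjusted and 69 / 68 / 67% adjusted.

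**Step 8: sensitivity to the seasonal model.** Take a linear date trend explaining 10 / 20 / 30% of variance, with d = 0.7 on the total SD. Independent dates give 76% power unadjusted and about 80 / 84 / 88% adjusted. A one-month shift gives bias of 0.16 / 0.22 / 0.27 SD and type I error of 10 / 14 / 19%. The direction is the same and the effects are larger.

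**The case against.** The strongest reply is that the protocol as written contains no demonstrated bias. Both groups share one study window, the recruitment channels are not split by age, and everyone is scheduled after the same phone screening. If dates are therefore unrelated to age, the tests are valid and the loss is small: 1 to 3 points of AUC power for the two smaller seasonal effects, and 8 points only for the largest. The larger distortions need shifts of 30 days or more. Covariates could also be left to an SAP, and the seasonal size is unknown.

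Much of this stands. Bias is a risk, not a fact. Chance imbalance does not add error either: with independent dates, a gap above 1.10 h in mean day length arises in 10% of studies, but this is already inside the 5%. The Background's contrast of office light (up to 300 lux) with sunlight (up to 100,000 lux) concerns indoors versus outdoors. Only section 6.2 speaks to season, and its winter-summer contrast is wider than a window ending in May.

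Two parts do not stand. The protocol is not silent on the analysis: it names unadjusted tests for its primary outcome. And parallel scheduling is a design matter that no SAP can supply once the data are collected.

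**Conclusion.** The concern holds and should be fixed. Analyses 1 and 2 omit a factor that the protocol itself expects to outweigh age, and the design does not balance it.

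- **Timing unrelated to age group:** the cost is precision only. AUC power falls from about 75% to 74, 72 or 67% as the assumed seasonal effect grows, and the hourly analysis loses between nothing and 6 points.
- **A 30-day drift:** AUC type I error is 6.4 to 11.7%, and the spurious difference is 0.10 to 0.22 SD.
- **A 15-day drift:** the effect is slight, with type I error at most 6.2%.

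All these sizes rest on assumed seasonal effects and shifts and on an assumed latitude. The direction does not depend on the particular values. Confidence in the size is moderate.

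**What to change.** 1. **Section 6.2:** beside the aim to match on sex, add an aim to schedule younger and older participants in parallel over the same calendar weeks. This is the main protection: at a 60-day shift, adjustment restores the type I error, but power is only about 60%.
2. **Section 8.4, analysis 1:** replace the unpaired t-test on AUC with a linear model of age group plus day length (or a smooth date term) at the participant's measurement dates. This is needed even with parallel scheduling, because the plain t-test is then conservative.
3. **Section 8.4, analysis 2:** add day length and its interaction with time of day.
4. **Section 8.4, analysis 3:** leave as it is.

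**Cost.** The AUC model uses 1 to 2 degrees of freedom. The hourly model uses 1 between subjects (error 58 to 57) and 23 within subjects (58 × 23 = 1334 to 57 × 23 = 1311). If the seasonal effect is small, the interaction term brings no gain in power (69.5% without it, 69.0% with it). Scheduling takes some effort. No extra participants or measurements are needed.
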